## **6. END OF STUDY**

### **6.1. Definition of End of Study**

This is an event driven trial. The end of the trial will be when the last data of the last patient required for the overall survival analysis has been received. Complete analysis will be done when all patients have completed week 52 or end of study visit and then every 52 weeks thereafter.

The study may also be prematurely terminated by the sponsor.

### **6.2. Criteria for Premature Withdrawal**

#### **Withdrawal from the study treatment /study**

The investigator can/must discontinue study treatment for a patient in the event of:

- Progressive disease (as per iRANO)
- Intercurrent illness
- Unacceptable toxicity (grade 3 or higher)
- Protocol violation
- Pregnancy
- Patient request
- In the case that the patient decides to prematurely discontinue study treatment he/she will be offered to continue into the Extended Safety Follow-up Phase
- In the case the patient decides not to or is unable to continue into the extended follow up phase then he/she will be withdrawn from the study. He /she will with the patient's permission be followed for survival assessment with monthly

telephone calls. Otherwise the patient will be considered lost to follow-up. The outcome of these discussions should be documented in both the medical records and in the CRF.

- Similarly, the investigator has the right to withdraw patients from the study in the event of intercurrent illness, unacceptable toxicity, protocol violation, pregnancy and administrative or other reasons. Patients have the right to withdraw from the study at any time for any reason.
- An excessive rate of withdrawals can render the study uninterpretable; therefore, unnecessary withdrawal of patients should be avoided.

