#### **Extended Safety Follow-up Phase:**

Patients who discontinue avelumab therapy for any reason at any point in the study will be entered into an extended safety follow-up period of 90 days. New treatment will then be at the investigator or local oncologist's suggestion. All subjects will be observed for the possible occurrence of delayed irAE's for survival data and information about subsequent therapies will be collected. Tissue samples in patients undergoing second surgical resections will be obtained for further biomarker analysis.

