### **9.3.4. Assessments at end of study**

An end of treatment study visit will occur when:

- 1) Grade 3 or higher avelumab related toxicity occurs
- 2) Evidence as per the iRANO criteria of tumor progression occurs and patient does not wish to continue treatment
- 3) Patient wishes for any reason to discontinue treatment or withdraw from the study. Clinical evidence of neurological deterioration resulting in an ECOG score

of at least 3 or more, unexplained by other comorbidities, unchanged by an increase in corticosteroid dose and sustained for at least two weeks.

A history, physical and neurological exam will be performed by a physician. Laboratory test as per schedule will be drawn. If any of the latter have already been performed to confirm the AE or tumor progression on the basis clinical neurological deterioration, then they need not be repeated.

A study specified gadolinium enhanced MRI or CT scan will be performed within 2 weeks of the end of study visit for all patients after 52 weeks.

Patients however who discontinue the study treatment on the basis of avelumab treatment related AE's or clinical evidence of tumor progression a study specified MRI or CT scan will be done at the discretion of the investigator.

Patients who prematurely discontinue study treatment will be encouraged to continue into the Extended Safety Follow-up phase of the study

Patients who not only end treatment but also withdraw from the study, for any reason, will be encouraged to have telephone follow ups every month in order to obtain survival information with regards to OS. Pathology samples will be obtained for repeat biomarker analysis if a second tumor surgery occurs

**NOTE:** Since the actual duration of pseudoprogression and the time for immunotherapies to become effective in patients with GBM are still unknowns patients will be allowed at the investigator and patient discretion to continue on study treatment after confirmation of radiographic progression unless there is significant drug toxicity Grade 3 or higher AE's unrelated to avelumab such as those secondary to intercurrent illness or temozolomide therapy do not constitute for the purpose of this study a reason to withhold avelumab therapy or withdraw the patient from the study.

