### **9.3.7. Follow-up**

All patients who discontinue from study treatment will be followed for survival information.

In addition, patients who withdraw from study treatment as a result of progressive disease all further anti-neoplastic treatment, (including surgery and re-irradiation) will be recorded until death or end of the study whichever occurs first.

Survival telephone visits will be performed every 4 weeks until death or the end of the study, whichever occurs first.

For patients who prematurely withdraw from study treatment without documented disease progression:

Disease assessments will be performed until disease progression is observed. All further anti-neoplastic treatment (including surgery and re-irradiation) will be recorded until death or end of the study whichever occurs first. Telephone survival visits will be performed every 4 weeks until death or the end of the study, whichever occurs first.

If the patient withdraws consent, this request must be documented in the source documents, and signed by the investigator. At this time, the patient will be asked if he/she agrees to be followed-up for collection of survival information. This agreement must be documented and signed by the investigator. The study staff may also use a public information source to obtain information about survival status.

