**Table 1: STUDY ACTIVITIES**

Tests and Evaluations	Screening Visit	Combination/ phase Week 0 to 24 Visit window: $\pm 2$ days														Monotherapy phase Week 26 to 52  Visit window: $\pm 2$ days														Extended safety follow-up phase 
		0	2	4	6	8	10	12	14	16	18	20	22	24	26	28	30	32	34	36	38	40	42	44	46	48	50	52		
Week	-12 to -1	0													26	28	30	32	34	36	38	40	42	44	46	48	50	52	EOS	
Informed Consent	X																													
Demographics Medical History	X																													
Physical Exam	X	X		X		X		X							X					X					X			X	X	
Neurological Exam	X	X		X		X		X							X					X					X			X	X	
Karnofsky	X	X																												
Vital Sign	X	X	X	X	X	X	X	X	X	X	X	X	X	X	X	X	X	X	X	X	X	X	X	X	X	X	X			
Lab's 	X	X	X	X	X	X	X	X	X	X	X	X	X	X	X	X	X	X	X	X	X	X	X	X	X	X	X			
ECOG	X	X	X	X	X	X	X	X	X	X	X	X	X	X	X	X	X	X	X	X	X	X	X	X	X	X	X			
MRI or CT scan		X																											X	X
P300		X																											X	X
AE's and concomitant medications		X	X	X	X	X	X	X	X	X	X	X	X	X	X	X	X	X	X	X	X	X	X	X	X	X	X	X		
Pre-infusion questionnaire		X	X	X	X	X	X	X	X	X	X	X	X	X	X	X	X	X	X	X	X	X	X	X	X	X	X			
Avelumab infusion Q 2 weeks		X	X	X	X	X	X	X	X	X	X	X	X	X	X	X	X	X	X	X	X	X	X	X	X	X	X			
Temozolamide		X		X		X		X		X		X		X		X		X		X		X		X		X				

See foot note on the next page

- 1 The Extended Safety phase will involve a site visit at day 30 and telephone follow-up at day 60 and 90 post end of treatment. A second site visit may be required if there is any concern
2. Patients who withdraw prematurely from the treatment or complete the 260 weeks of treatment will be offered to enter the Extended safety follow-up phase
3. Lab's: **Hematology** will include Hemoglobin, platelet count, WBC count, absolute neutrophils, and lymphocytes. **Coagulation** will include INR, and aPTT (at screening or baseline only). **Blood chemistry** will include total bilirubin, AST, ALT, LDH, alkaline phosphatase, serum albumin, phosphate, serum creatinine, and electrolytes (sodium, potassium, calcium), glucose, amylase, lipase, TSH, GGT, CK. **Urinalysis** will include urine dipstick test. **Serum  $\beta$ -HCG** must be performed at screening in women of childbearing potential. Subsequent **urine  $\beta$ -HCG** must be collected monthly. Additional tests may be done at the discretion of the investigator for patient safety.
- TSH T4 will be collected Q8weeks and repeated at the Extended Safety visit

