## **12. STATISTICAL STATEMENT AND ANALYTICAL PLAN**

### **12.1. Sample Size Considerations**

A convenience sample of thirty (30) patients is based on recruitment feasibility. This sample size will permit estimation of dichotomous outcome rates with margins of error of less than 18% (based on a significance level of 0.05) and estimation of continuous parameter means to within 0.36 standard deviations. This is an early stage study, so analysis will focus on descriptive statistics. Continuous parameters will be summarized by means and 95% confidence intervals or by medians and

interquartile ranges, as appropriate. Dichotomous outcomes will be summarized with point estimates of the rate, as well as 95% confidence intervals. Time-to-event data will be summarized using Kaplan-Meier curves.

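### Section 6.2 lets patients be taken out of the study, not only off treatment, for toxicity or illness, and the 90-day safety follow-up is automatic in some places and optional in others, so post-treatment data can be lost selectively

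*Protocol*

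**What the plan says.** **Leaving the study.** Protocol section 6.2 first lists reasons to stop study treatment. It then adds a separate right: "Similarly, the investigator has the right to withdraw patients from the study in the event of intercurrent illness, unacceptable toxicity, protocol violation". The list closes with two further grounds, administrative matters and pregnancy, and leaves room for others. The same section removes from the study a patient who declines, or is unable, to go on to extended follow-up. Survival calls then need the patient's permission; without it the patient counts as lost to follow-up.

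**Safety follow-up.** Three strengths of wording appear:
- Automatic, in section 4.2 and likewise the synopsis: "Patients who discontinue avelumab therapy for any reason at any point in the study will be entered into an extended safety follow-up period".
- Offered, in Table 1, footnote 2: such patients "will be offered to enter the Extended safety follow-up phase". Section 6.2 also offers it, for patients who themselves decide to stop.
- Encouraged, in section 9.3.4: "Patients who prematurely discontinue study treatment will be encouraged to continue into the Extended Safety Follow-up phase of the study".

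**Survival follow-up.** Section 9.3.7 is unconditional: "All patients who discontinue from study treatment will be followed for survival information". It also continues disease assessments to progression in those who stop treatment without it. Withdrawn consent is the only exception it names.

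**Other immunosuppressants.** Section 8.4 does not allow them and makes their use a reason for study withdrawal. Table 3 names such agents for severe or non-improving immune-related events.

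**SAP.** It does not say how withdrawn patients or incomplete safety follow-up are handled.

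**The concern.** Stopping a drug for toxicity is a treatment decision. Ending data collection for toxicity makes missingness depend on an outcome the trial measures. Here safety is the primary objective, and the extended phase exists to observe delayed immune-related events. Patients removed for toxicity or illness are unlikely to resemble the rest, so their missing data cannot be assumed ignorable.

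The outcomes at stake come after the last dose: late immune-related events, whether and when events resolve, progression, and survival. Table 3 uses steroid tapers of at least a month and has a category for events lasting 12 weeks or longer, so these courses can outlast treatment. With 30 patients and fixed cut-offs of 21 (one-year survival) and 11 (one-year progression-free survival), a few untraced patients can matter.

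**Working it through.** **1. Which rule applies?** Take a patient whose avelumab is stopped for toxicity.
- Under 4.2 and 9.3.7: 90 days of safety follow-up, then survival follow-up.
- Under Table 1 and 9.3.4: safety follow-up only if the patient accepts.
- Under 6.2: the investigator may end study participation, after which survival calls need permission.
- Under 8.4, if another immunosuppressant was used: study withdrawal.

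No passage says which of these prevails.

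**2. Which outcomes are exposed?** The primary endpoint (Protocol 12.3.1, SAP 1.3.1) rests on avelumab-related adverse events that lead to permanent or transient discontinuation. Such an event is recorded before a withdrawal for toxicity can follow it, so that count is not exposed. Resolution, delayed immune-related events, and progression or survival status are.

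**3. The plan's precision figure.** Protocol 12.1 says "A convenience sample of thirty (30) patients is based on recruitment feasibility" and claims "margins of error of less than 18% (based on a significance level of 0.05". With a rate of 50%, the half-width is 1.96 × √(0.25/30) = 0.179, or 17.9 points, so the claim reproduces. The full width is 2 × 17.9 = 35.8, about 36 points.

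**4. Effect of untraced patients.** The documents give no withdrawal rate, so I assume L = 1 to 3 of 30. With x events seen, the rate lies between x/30 and (x + L)/30, a range of L/30.

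| L | Range L/30 | x = 2 delayed events (assumed) | Half-width if only 30 − L are analysed | Exact 97.5% upper limit if no event is seen |
|---|---|---|---|---|
| 0 | 0 | 6.7% | 17.9 points | 11.6% |
| 1 | 3.3 points | 6.7% to 10.0% | 18.2 points | 11.9% |
| 3 | 10.0 points | 6.7% to 16.7% | 18.9 points | 12.8% |

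The half-width is 1.96 × √(0.25/(30 − L)); the upper limit is 1 − 0.025^(1/(30 − L)). One loss takes the half-width past the stated 18 points. Like for like, the 10-point range at L = 3 compares with the 35.8-point full width: 10/35.8 = 28%.

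**5. Direction for survival.** Suppose 18 patients are known alive at one year, 9 known dead and 3 untraced (an illustration).
- Untraced counted as deaths: 18/30 = 60.0%, the plan's no-effect rate.
- Untraced dropped: 18/27 = 66.7%.
- Untraced counted as alive: 21/30 = 70.0%, which meets the cut-off.

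The same data give opposite conclusions. If 3 losses unrelated to outcome are counted as deaths, an assumed true rate of 75% becomes 0.75 × 27/30 = 67.5%, and the chance of at least 21 survivors falls from 0.803 to 0.470. At the 60% no-effect rate it falls from 0.176 to 0.056. That convention works against avelumab. Protocol 5.2 censors patients lost to follow-up in the time-to-event definitions, but the count rules in Protocol 12.3.2 and SAP 1.3.2 do not say how a patient of unknown status is counted.

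**The case against.** The strongest reply is that section 6.2 permits study withdrawal without requiring it and warns against unnecessary withdrawals, while other sections already protect most of the data. Section 9.3.7 provides survival calls every four weeks, continued disease assessment, and public sources for survival status. Section 9.3.4 encourages monthly calls even after study withdrawal. Section 11.13 requires resolution dates and persistent follow-up of serious events. Section 2 reports no treatment-related immune-mediated events in the cited phase I trial with onset more than 30 days after the last dose.

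Most of this stands and limits the expected loss. It does not settle the conflict: nothing says 9.3.7 overrides 6.2, section 8.4 words its study withdrawal as a consequence rather than an option, and the protocol chose a 90-day window despite the phase I result.

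A reader might go further and infer three things that the documents do not support:
- *That these patients are lost and the primary result is biased.* The text allows loss without making it certain, and the discontinuing event is already counted.
- *That one-year survival and PFS are biased in avelumab's favour.* Against a fixed count of 21 or 11 of 30, an untraced patient is not a confirmed success, so the bias can run the other way. No passage says patients with toxicity fare worse; the link between immune-related events and survival is an exploratory question.
- *That about 3 patients will be lost, because section 2 cites 9.5% treatment-related Grade 3 or higher events (30 × 0.095 = 2.85).* That is an event rate, not a loss rate.

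**Conclusion.** The point holds as an internal conflict that permits outcome-dependent loss of post-treatment data. It is more than missing detail, because section 6.2 states a rule that can end data collection on account of toxicity or illness. Exposed are delayed immune-related events, event resolution, and progression or survival status where the patient gives no permission.

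The size is modest and conditional: 3 to 10 points on a follow-up-dependent rate if 1 to 3 of 30 patients are untraced, which is an assumption. Bias in the primary count is not shown, and the direction of any effect on overall or progression-free survival is open until the SAP says how untraced patients count. The change should be made because it is cheap and the loss is avoidable.

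**What to change.** - **Section 6.2:** separate stopping study treatment from leaving the study. Limit investigator-initiated withdrawal to study treatment for every listed reason, including pregnancy and administrative grounds.
- **Sections 6.2 and 9.3.4 and Table 1:** use the rule of 4.2 and 9.3.7. Everyone who stops avelumab enters the 90-day safety follow-up and then survival follow-up by default. Only the patient's own withdrawal of consent to follow-up ends data collection.
- **Section 8.4 and Table 3:** reconcile the study-withdrawal wording with the agents the table names. Which clinical rule should apply is for the sponsor to settle.
- **SAP:** keep all treated patients in the denominators, state how patients of unknown one-year status count towards the 21 and 11 cut-offs, and report how many complete the 90 days.

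The cost is protocol, SAP and consent wording. The day-30 visit, the day-60 and day-90 calls and the four-weekly survival calls are already scheduled.

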## **7. STUDY POPULATION**

Patients with newly diagnosed glioblastoma histologically confirmed with surgical resection or biopsy, who will be undergoing or have finished the standard temozolomide/radiotherapy no more than 3 weeks ago.

### **7.1. Inclusion criteria**

1. Signed informed consent
2. Age  $\geq$  18 years
3. Present with newly diagnosed supratentorial Glioblastoma (GBM) with a tissue diagnosis that has been established following either a surgical resection or biopsy. This includes treatment-naïve - (chemotherapy and radiotherapy)- patients with prior diagnosis of a lower grade astrocytoma that has been upgraded to a histologically verified GBM
4. Karnofsky performance score of 70 or higher
5. Patients entering the study must be on a stable dose of no more than 12 mg (maximum) of Dexamethasone (or equivalent) daily for symptoms related to cerebral edema
6. Will be or is undergoing or has received the standard therapy of chemo radiation therapy (60Gy in 30 fractions of 2Gy/day or as per local protocol with concurrent temozolomide of 75mg/m^2 per day PO or as per local practise) no more than 21 days ago
7. Has not yet begun but will begin standard monthly temozolomide therapy
8. Patient must have at least 1 formalin fixed paraffin embedded tumor tissue block representative of glioblastoma available for biomarker analysis and determination of MGMT status (if not already done). If tumor block is not available or not of adequate quality, sufficient pathology material, representative of glioblastoma, must be available
9. Adequate hematological function defined by absolute neutrophil count (ANC)  $\geq$  1.5  $\times$  10^9/L, platelet count  $\geq$  100  $\times$  10^9/L, and hemoglobin  $\geq$  9 g/dL (may have been transfused)
10. Adequate hepatic function defined by a total bilirubin level  $\leq$  1.5  $\times$  the upper limit of normal (ULN) range and AST and ALT levels  $\leq$  2.5  $\times$  ULN for all subjects

11. Adequate renal function defined by an estimated creatinine clearance  $\geq$  30 mL/min according to the Cockcroft-Gault formula (or local institutional standard method)
12. Negative serum pregnancy test at screening for women of childbearing potential
13. Highly effective contraception for both male and female subjects if the risk of conception exists. (Note: The effects of the trial drug on the developing human fetus are unknown; thus, women of childbearing potential and men able to father a child must agree to use 2 highly effective contraception, defined as methods with a failure rate of less than 1 % per year. Highly effective contraception is required at least 28 days prior, throughout and for at least 30 days after avelumab treatment.)
14. International normalized ratio (INR) or PT (secs) and activated partial thromboplastin time (aPTT):
  - in the absence of therapeutic intent to anticoagulate the subject: INR $\leq$ 1.5 or PT  $\leq$ 1.5 x ULN and aPTT  $\leq$ 1.5 x ULN
  - in the presence of therapeutic intent to anticoagulate the subject: INR or PT and aPTT within therapeutic limits (according to the medical standard in the institution)

*NOTE:* Use of full-dose anticoagulants is permitted as long as the INR or aPTT is within therapeutic limits (according to the medical standard in the institution) and the patient has been on a stable dose of anticoagulants for at least two weeks prior to baseline.
15. Willing and able to comply with the protocol as judged by the Investigator

## 7.2. Exclusion Criteria

1. Patients who have evidence of leptomeningeal disease
2. Known significant pulmonary, cardiovascular, hepatic disorders or any other disease that in the opinion of the investigator would be contraindicated to receive anti PD-L1 therapy such as avelumab,
3. "Clinically significant (i.e., active) cardiovascular disease: cerebral vascular accident/stroke (< 6 months prior to enrollment), myocardial infarction (< 6 months prior to enrollment), unstable angina, congestive heart failure ( $\geq$  New York Heart Association Classification Class II), or serious cardiac arrhythmia requiring medication."
4. Prior treatment with bevacizumab or any checkpoint immune blockade therapies
5. Any other concomitant immunosuppressant other than temozolomide and steroids or any recent (within 3 months) experimental therapy
6. Patients who have finished their radiotherapy course more than 3 weeks prior to baseline
7. Prior organ transplantation, including allogeneic stem-cell transplantation
8. Significant acute or chronic infections including, among others:
  - Known history of testing positive test for human immunodeficiency virus (HIV) or known acquired immunodeficiency syndrome (AIDS),

- Positive test for HBV surface antigen and / or confirmatory HCV RNA (if anti-HCV antibody tested positive),
- 9. Active autoimmune disease that require ongoing corticosteroid and/or immunosuppressant therapy that might deteriorate when receiving an immunostimulatory agent:
  - Subjects with diabetes type I, vitiligo, psoriasis, hypo- or hyperthyroid disease or any other autoimmune disease not requiring immunosuppressive treatment are at the investigator's discretion eligible
  - Subjects requiring hormone replacement with corticosteroids are eligible if the steroids are administered only for the purpose of hormonal replacement and at doses  $\leq$  10 mg or 10 mg equivalent prednisone per day
  - Administration of steroids through a route known to result in a minimal systemic exposure (topical, intranasal, intro-ocular, or inhalation) are acceptable
- 10. Known severe hypersensitivity reactions to monoclonal antibodies (Grade  $\geq$  3 NCI-CTCAE v 4.03), any history of anaphylaxis, or uncontrolled asthma (that is, 3 or more features of partially controlled asthma)
- 11. Pregnancy or lactation
- 12. Known alcohol or drug abuse
- 13. Any psychiatric or cognitive condition that would prohibit the understanding or rendering of informed consent
- 14. Vaccination within 4 weeks of the first dose of avelumab and while on trial is prohibited except for administration of inactivated vaccines
- 15. Any other malignancy within 5 years prior to baseline, except for adequately controlled limited basal cell carcinoma of the skin, squamous carcinoma of the skin or carcinoma in situ of the cervix
- 16. Evidence of any active infection requiring hospitalization or IV antibiotics within 2 weeks prior to baseline.
- 17. Persisting toxicity related to prior therapy (NCI CTCAE v. 4.03 Grade  $>$  1); however, alopecia, sensory neuropathy Grade  $\leq$  2, or other Grade  $\leq$  2 not constituting a safety risk based on investigator's judgment are acceptable.
- 18. Other severe acute or chronic medical conditions including colitis, inflammatory bowel disease, pneumonitis, pulmonary fibrosis or psychiatric conditions including recent (within the past year) or active suicidal ideation or behavior; or laboratory abnormalities that may increase the risk associated with study participation or study treatment administration or may interfere with the interpretation of study results and, in the judgment of the investigator, would make the patient inappropriate for entry into this study.

